Both acute and chronic in vivo studies have been conducted with GCGR antibodies in normal mice, insulin-resistant diet-induced obesity (DIO) mice, and leptin-deficient *ob/ob* mice. Administration of GCGR antibodies lowered blood glucose in a dose-dependent fashion without inducing hypoglycemia in normal, DIO, and *ob/ob* mice. In a study conducted in normal cynomolgus monkeys, a single SC injection of the REMD-477 analog, 2-59.1, resulted in improved glucose tolerance as well as increased glucagon and GLP-1 levels. In the streptozotocin-induced T1DM model in mice, REMD2.59C (an REMD-477 analog) treatment totally corrected severe hyperglycemia (~500 mg/dL) after just the first weekly dose, normalized the HbA1c level to < 5%, and increased insulin immunostaining area in the islets, after 12 weekly doses of REMD-477 ([Pharmaron, 2014](#)). In another T1DM model induced by alloxan-injection in mice, an analog of REMD-477 (mAb Ac) corrected hyperglycemia after the 1st weekly injection, and normalized phosphorylated cAMP response element binding protein (p-CREB), a transducer of the glucagon signal, and suppressed phosphoenolpyruvate carboxykinase (PEPCK), a key enzyme in gluconeogenesis ([Wang, 2015](#)).

In chronic rodent studies, the chimeric murine GCGR neutralizing antibody GR15c was used as a surrogate to assess the effects of blocking the glucagon pathway on hyperglucagonemia, alpha cell hyperplasia, and beta cell function. GR15c treatment caused dose-dependent hyperglucagonemia and minimal to mild alpha cell hyperplasia due to adaptive compensation for the reduced GCGR signal. There was no evidence in these studies of pancreatic alpha cell neoplastic transformation in mice treated with GR15c for as long as 18 weeks. Both treatment-induced hyperglucagonemia and alpha cell hyperplasia were reversible after treatment withdrawal for periods of 6 and 10 weeks. Importantly, pancreatic beta cell function was preserved, as demonstrated by improved glucose tolerance throughout the 18-week treatment period.

Preclinical Studies

Preclinical Pharmacokinetics

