The standard meal consists of 2 servings [8 fluid ounces (237 mL)/ serving] of liquid Ensure Plus containing a total of 700 kcal. The total mixed-meal serving will be broken up into 4 equal portions, and each portion will be served every 5 minutes. The entire meal should be consumed within a 15-minute period. Water and non-caffeinated, calorie-free beverages may be consumed ad libitum. During the MMTT, C-peptide, glucagon, insulin, GLP-1 (active and total), and glucose concentrations will be measured 10 minutes before (time-10) and just before (time 0) initiating mixed-meal ingestion and at 30, 60 and 120 minutes after initiating mixed meal ingestion. Stimulated C-peptide will be measured with the ultra-sensitive C-peptide kit from Mercodia.

Arginine Challenge Test: Part A only (prior to Amendment #1)

For a subset of subjects enrolled in Part A prior to Protocol Amendment #1, the arginine challenge test will be performed during the Overnight Baseline Visit, Day 85, and Day 162 immediately after the completion of the MMTT. The 120 minute time-point completion for the preceding MMTT, will also serve as time zero (0) for the Arginine Challenge Test.

An intravenous injection of 5 g of arginine (given as 50 mL volume of a 10% arginine HCl solution) will be administered over 30 to 60 seconds, with time 0 set halfway through the arginine injection. Samples for plasma glucose, glucagon, C-peptide, and GLP-1 will be collected from the contralateral arm at 2, 3, 4, 5, 7, and 10 min after the arginine injection. After the last draw at 10 minutes, the IV insulin infusion can be discontinued and subjects will be instructed on how to resume their usual insulin therapy per protocol.

For all other subjects enrolled in Part A or are ongoing at the time of the Protocol Amendment #1, the arginine challenge test will not be conducted.

Seven-Point Blood Glucose Profile

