10 STATISTICAL METHODOLOGY

10.1 General

Data listings will be provided for the All Subjects Population. Summary statistics and statistical analyses will be performed for subjects included in the relevant analysis populations (Safety/PK/PD).

For continuous data, summary statistics will include the arithmetic mean, arithmetic standard deviation, median, minimum, maximum, and number. For log-normal data (eg, the Mixed Meal Tolerance Test [MMTT] parameters: areas under the concentration-time curve [AUCs]), the geometric mean and geometric coefficient of variation (CV%) will also be presented. For categorical data, frequency counts and percentages will be presented. Data listings will be provided for all subjects. For the calculation of summary statistics and statistical analysis, unrounded data will be used.

Outputs will be created separately for Parts A and B.

Missing values will not be imputed.

Data analysis will be performed using SAS® Version 9.4.

Analysis Data Model (ADaM) datasets will be prepared using Clinical Data Interchange Standards Consortium (CDISC) ADaM Version 2.1, and CDISC ADaM Implementation Guide Version 1.1. Pinnacle 21 Community Validator Version 2.2.0 will be utilized to ensure compliance with CDISC standards.

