10.3.4.3 Fasting Glucose, MMTT and Arginine Challenge Test – Part A only

The following section applies to Part A only.

The fasting glucose concentrations, concentrations following the MMTT and Arginine Challenge Test (ACT), will be summarized by treatment group and timepoint, along with changes from baseline. The percentage changes from baseline for fasting glucose concentrations will also be summarized by treatment group and timepoint. Figures of mean profiles, changes and percentage changes from baseline will be presented by treatment. The baseline fasting glucose is the last value measured prior to the first study drug dosing. The MMTT baseline is the average value from the -10 minute and -1 minute timepoints for each MMTT. The ACT baseline is the 0 minute timepoint, which is equivalent to the 120 minute timepoint of the MMTT.

The difference in glucose concentration following MMTT will be derived as the glucose concentration at the 120 minute timepoint at MMTT, minus the MMTT baseline glucose concentration. This metric will be summarized by treatment group and study day, along with changes from baseline, where baseline is the defined as the metric obtained at the Lead-in (OBV) period for those subjects enrolled prior to amendment # 1 of the protocol or the baseline visit for those thereafter.

Concentrations of glucose, c-peptide, glucagon, insulin, GLP-1 (active and total) will be used to derive the respective AUC (unadjusted and adjusted by test baseline) from the MMTT and ACT for each study day.

AUC will be calculated using the linear trapezoidal method. To calculate AUC adjusted for baseline, the baseline concentration value will be subtracted from all post-test concentrations. Any negative values after baseline adjustment will be set to zero.

AUC calculations, where possible, will be carried out using actual post-dose times recorded in the raw data. If actual times are missing, nominal times may be used with sponsor approval. The baseline for AUC of each parameter is the value derived from the concentrations obtained at the Lead-In (OBV) period for those subjects enrolled prior to Amendment # 1 of the protocol or the baseline visit for those thereafter.

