The change from baseline measurements for fasting glucose, the change from baseline difference in glucose concentration following MMTT, and the change from baseline of the derived AUC for glucose, C-peptide, glucagon, insulin and GLP-1 (active and total), unadjusted and adjusted by test baseline, will be statistically analyzed. The percentage change from baseline for the derived AUC, unadjusted and adjusted by test baseline for C-peptide, will also be statistically analyzed. A repeated measures ANCOVA will be used to compare the each of these parameter between treatment groups for each timepoint. Dependent variables will be treatment, day, and the treatment by day interaction. The baseline variable will be used as a covariate. Covariates may be added to the above model depending on the results from the comparison of baseline characteristics as detailed in section 10.3.4.1

Subject will be used as a random effect. The LS mean for each treatment will be presented for each timepoint. Also, the difference from placebo, the 95% CI of the difference from placebo, and p-value associated with the null-hypothesis of no difference will be reported for each timepoint.

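### Setting negative baseline-adjusted values to zero makes the planned percentage change in adjusted C-peptide AUC undefined for some subjects, and can bias the adjusted glucagon and GLP-1 AUCs

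*SAP*

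**What the plan says.** SAP 10.3.4.3 derives AUCs by the linear trapezoidal method for glucose, C-peptide, glucagon, insulin and GLP-1, with and without adjustment for the test baseline. For the adjusted version, "the baseline concentration value will be subtracted from all post-test concentrations", and then "Any negative values after baseline adjustment will be set to zero". Change from baseline in both versions is tested for every analyte. For C-peptide there is a further analysis: "The percentage change from baseline for the derived AUC, unadjusted and adjusted by test baseline for C-peptide, will also be statistically analyzed".

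SAP 10.1.1 defines percentage change with the subject's own pre-treatment value as denominator and gives no rule for a zero. SAP 10.1 imputes nothing. It treats MMTT AUCs as an example of log-normal data, for which "the geometric mean and geometric coefficient of variation (CV%) will also be presented", without separating adjusted from unadjusted AUCs.

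Eligibility requires fasting C-peptide below 0.7 ng/mL, with no lower limit. On the drug's effect on hormone levels, Protocol section 2 says that an analog in monkeys "resulted in improved glucose tolerance as well as increased glucagon and GLP-1 levels".

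**The concern.** Clipping keeps scatter above the baseline and discards scatter below it. Two things follow.

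First, if every post-meal sample lies at or below the baseline, the adjusted AUC is exactly zero. For C-peptide that value can become the denominator of a tested percentage change, in a population where flat responses are plausible. It also defeats a geometric mean.

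Second, a flat profile that escapes zero always gives a positive AUC, whose size follows the scatter. If scatter rises with concentration and the drug raises glucagon or GLP-1, the active arms could show a larger adjusted AUC at Week 13 with no change in meal response. The C-peptide, glucagon and GLP-1 AUCs are the secondary measures of beta and alpha cell function.

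**Working it through.** The plan gives no figure for this rule, so there is none to reproduce.

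**Inputs from the documents.** Two pre-meal samples, averaged; post-meal samples "at 30, 60 and 120 minutes after initiating mixed meal ingestion"; 75 subjects in Part A, 25 per arm (SAP 8); two-sided 0.05 (SAP 10.3.4.1 code).

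**Assumptions.** Independent normal scatter with SD s at each sample. The documents give no within-test CV, no human fold-rise and no response size.

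**1. Chance of an adjusted AUC of exactly zero, no true response.** Each difference (post-meal sample minus the mean of two) has variance 1.5s². Any two share covariance 0.5s², so the correlation is 1/3. The chance that all three are at or below zero is 1/8 + (3/4π)·arcsin(1/3) = 0.125 + 0.2387 × 0.3398 = 0.206. If the time-0 sample also enters the trapezoid as its own point, it must not exceed the -10 sample. That has chance 1/2, independent of the rest, giving 0.103. The SAP does not say which applies. Neither figure depends on the CV. With a true response of 1, 1.5 or 2.5 within-test SDs, the 20.6% falls to 3.4%, 1.0% or 0.04%.

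**2. Undefined percentage changes among 75 subjects** (75 × share with no response × probability of zero):

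| Share with no response | at 10.3% | at 20.6% |
|---|---|---|
| 10% | 0.8 | 1.5 |
| 25% | 1.9 | 3.9 |
| 50% | 3.9 | 7.7 |
| 100% | 7.7 | 15.5 |

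At a 25% share, the chance of at least one is 1 − (1 − 0.25 × 0.103)^75 = 86%, or 98% with 0.206.

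**3. Near-zero denominators.** For flat profiles with a non-zero pre-treatment AUC, simulated percentage change from noise alone runs from -100% (5th centile) to about +1,400% (95th).

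**4. Mean clipped AUC of a flat profile.** Each post-meal difference contributes s·√1.5/√(2π) = 0.489s on average, with trapezoid weights 30 + 45 + 30 = 105 min: 51.3s. The time-0 point adds 0.282s × 15 min = 4.2s. The total is 55.5s min = 0.926s h. At 15% CV this is 0.139 of level × h. At a 3-fold level it is 0.417 if s is proportional to level, and still 0.139 if s is constant. Without clipping the mean is 0, and the SD is s·√(60² + 45² + 30² + 45² + 30²) = 97.2s min = 1.62s h, or 0.243 at 15% CV. The clipped SD is 0.137.

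**5. False-positive rate, adjusted AUC.** Simulated ANCOVA of change on treatment and baseline AUC, 25 per arm, same absolute meal rise in both arms, assumed 15% CV proportional to level unless stated:

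| Meal rise (share of placebo level) | 2-fold | 3-fold | 5-fold |
|---|---|---|---|
| none | about 50% | about 86% | about 98% |
| 30% | about 16% | about 41% | about 79% |
| 50% | about 7% | about 13% | about 41% |
| 100% | about 6-13% across the range | | |
| any, constant-SD scatter (10% and 20% CV runs) | 3.5-5.8% | | |

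Without clipping, rates stay at about 5% in the proportional-scatter cases. Rates for a non-zero rise also depend on the assumed shape of the meal curve, so they show order of magnitude only.

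**The case against.** **Glucagon and GLP-1.** The strongest case is against this limb. Inflation needs scatter that grows with level; constant-SD scatter gives none. The log-normal description of MMTT AUCs fits proportional scatter but does not establish it. The highest rates also need no meal response at all in a 700-kcal test. The protocol's animal evidence on glucagon is mixed: raised in rats and after an analog in monkeys, but no clear effect in the monkey toxicology studies. No human figure is given. If the meal response itself scales with level, the unclipped AUC rejects too (87% and 99% of simulated trials at 2- and 3-fold), and that difference is real. All of this stands.

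**Consequence.** Unadjusted AUCs are tested in parallel and fasting levels separately. The endpoint list does not say that the adjusted AUC is the endpoint. A reader might infer that falls in glucose are lost, but SAP 10.3.4.3 also tests the 120-minute minus baseline glucose difference without clipping. Absolute change in adjusted C-peptide AUC keeps every subject with both tests. A zero only at Week 13 gives -100%, not an undefined value. A pre-treatment zero arises before dosing, so the loss should be balanced across arms in expectation; what changes is the population described, and precision.

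**What this does not answer.** The percentage change still lacks a rule for a zero denominator. The general clause in SAP 10.3.4.1 on transformations and non-parametric methods does not help: zeros cannot be logged, an undefined percentage cannot be ranked, and a rank test would still see a clipping shift.

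**Sample times.** The SAP says "The MMTT baseline is the average value from the -10 minute and -1 minute timepoints for each MMTT", while the protocol draws samples "10 minutes before (time-10) and just before (time 0) initiating mixed-meal ingestion". A reader might infer that a required sample is never taken. The protocol's time-0 sample is itself taken just before the meal, so this is a labelling matter.

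**Conclusion.** The C-peptide point holds and needs no assumption about the drug. Among subjects with detectable values and no response, about 10-20% will have an adjusted AUC of exactly zero. The tested percentage change is then undefined if the zero is pre-treatment, and erratic if the denominator is merely small. The number affected depends on the share of non-responders, which the documents do not give: roughly 2 to 4 of 75 if a quarter have no response. More would be affected if profiles lie below quantification, for which no substitution rule is stated. Geometric means of adjusted AUCs fail on the same zeros.

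The glucagon and GLP-1 point holds only conditionally. A reader might infer that, because the drug raises these hormones, the plan will produce a false meal-response effect. The documents do not support that: the scatter model, the fold-rise and the response size are all assumed, and within plausible assumptions the false-positive rate runs from about 5% to about 98%. What can be said is that clipping can bias this comparison upward, and that leaving negatives in place avoids the bias.

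The effect is confined to some of the secondary summaries in Part A. The primary endpoint is not affected. The change should be made because it is cheap, not because the trial's main conclusion is at risk.

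**What to change.** In SAP 10.3.4.3 and 10.1:

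1. Delete the percentage-change analysis of the adjusted C-peptide AUC. Keep absolute change for the adjusted AUC and percentage change for the unadjusted AUC. State a value for below-quantification samples so that the unadjusted AUC cannot be zero. Removing the clip alone would not rescue the deleted analysis, since a net AUC can be near zero or negative.
2. Give geometric mean and CV% for unadjusted AUCs only.
3. Retain negative values (net incremental AUC) in the adjusted AUC that is tested, and present the clipped version as supportive.
4. As a minor alignment, label the MMTT baseline samples -10 and 0 minutes to match the protocol.

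The cost is SAP wording and derivation code, plus a wider SD for the net AUC: about 0.24 against 0.14 of level × h for a flat profile at an assumed 15% CV. No data collection changes.

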10.3.4.4 Continuous Glucose Monitoring and Seven-point Glucose Profile

The following mean and changes from baseline in parameters from the CGM and seven-point glucose profile assessment will be summarized separately for Parts A and B by treatment. For the Average Daily 24-h Glucose Concentration, the percentage changes from baseline will also be summarized separately for Parts A and B by treatment.

- Average Daily 24-h Glucose Concentration
 - Derived as the average 24-h glucose concentration, over the course of 7 days or 3 days, for CGM and seven-point glucose respectively.
- Time within Target Range (70-180 mg/dL), Time lower than Target Range (<70 mg/dL) and Time higher than Target Range (> 180 mg/dL)
 - Derived as the percentage of time for which the glucose concentration falls into these corresponding ranges, over the course of 7 days for CGM
 - Derived as the summation of time intervals where the glucose concentration falls into these corresponding ranges, divided by the total assessed time, and expressed as a percentage, for the seven-point glucose assessment.

The changes from baseline values will be statistically analyzed by part. For the Average Daily 24-h Glucose Concentration, the percentage changes from baseline will also be statistically analyzed by part. The baseline for CGM parameters is defined as the average value obtained from the Lead-In (Part A – 14 to 28 days; Part B – 7 to 14 days) period. The baseline for seven-point glucose is defined as the average obtained from the three consecutive days during the Lead-In (2 to 4 weeks) period.

A repeated measures ANCOVA will be used to compare the change from baseline values for the above parameters between treatment groups for each timepoint for Parts A and B separately. Dependent variables will be treatment, day, and the treatment by day interaction. The baseline variable will be used as a covariate. Covariates may be added to the above model depending on the results from the comparison of baseline characteristics as detailed in section [10.3.4.1](#).

Subject will be used as a random effect. The LS mean for each treatment will be presented for each timepoint. Also, the difference from placebo, the 95% CI of the difference from placebo, and p-value associated with the null-hypothesis of no difference will be reported for each timepoint.

Although CGM will be conducted throughout the study from Dose 1 through EOS visit for safety monitoring and insulin use adjustments, the CGM data collected during the one week periods following Doses 4, 8, and 12 and during wash-out on Weeks 16 and 20 will be analyzed.

The ratio of average glucose obtained from the CGM at Day 78 (Week 12) and Baseline will be multiplied against the ratio of average daily insulin use obtained from the insulin diary at Day 78 (Week 12) and Baseline. This metric will be derived as described below and summarized by treatment.

$$\frac{\text{Average Daily Glucose from CGM at Week 12}}{\text{Average Daily Glucose from CGM at Baseline}} * \frac{\text{Average Daily Insulin Use at Week 12}}{\text{Average Daily Insulin Use at Baseline}}$$

For Parts A and B separately an ANOVA will be used to compare the values for the above metric between treatment groups. Dependent variables will be treatment. Covariates may be added to the above model depending on the results from the comparison of baseline characteristics as detailed in section 10.3.4.1.

The LS mean for each treatment will be presented. Also, the difference from placebo, the 95% CI of the difference from placebo, and p-value associated with the null-hypothesis of no difference will be produced.

10.3.4.5 Insulin, C-peptide, GLP-1 (active & total) and Glucagon

The insulin, C-peptide, GLP-1 (active & total) and glucagon concentrations will be summarized separately for Parts A and B by treatment group and timepoint, along with changes from baseline. Figures of parameter means and changes from baseline will be presented by treatment. The baseline assessment for Part A subjects is defined as the measurement taken at the Lead-In (OBV) period for those subjects enrolled prior to Amendment # 1 of the protocol or the baseline visit for those thereafter. For subjects enrolled in Part B the baseline assessment is defined as the last assessment taken prior to Day 1 dosing.

The respective change from baseline measurements for C-peptide, GLP-1 (active & total) and glucagon will be statistically analyzed for Part A subjects only. The respective change from baseline measurements for insulin will be statistically analyzed for Part A and B separately. A repeated measures ANCOVA will be used to compare each parameter between treatment groups for each timepoint. Dependent variables will be treatment, day, and the treatment by day interaction. The baseline variable will be used as a covariate. Covariates may be added to the above model depending on the results from the comparison of baseline characteristics as detailed in section 10.3.4.1.

Subject will be used as a random effect. The LS mean for each treatment will be presented for each timepoint. Also, the difference from placebo, the 95% CI of the difference from placebo, and p-value associated with the null-hypothesis of no difference will be reported for each timepoint.

10.3.4.6 HbA1c

The HbA1c concentrations will be summarized separately for Parts A and B by treatment group and timepoint, along with changes from baseline. The baseline assessment for Part A subjects is defined as the measurement taken at the Lead-In (OBV) period for those subjects enrolled prior to Amendment # 1 of the protocol or the baseline visit for those thereafter. For subjects enrolled in Part B the baseline assessment is defined as the last assessment taken prior to Day 1 dosing..

The changes from baseline for HbA1c will be statistical analyzed separately for Parts A and B. A repeated measures ANCOVA will be used to compare changes between treatment groups for each timepoint. Dependent variables will be treatment, day, and the treatment by day interaction. The baseline variable will be used as a covariate. Covariates may be added to the above model depending on the results from the comparison of baseline characteristics as detailed in section [10.3.4.1](#).

Subject will be used as a random effect. The LS mean for each treatment will be presented for each timepoint. Also, the difference from placebo, the 95% CI of the difference from placebo, and p-value associated with the null-hypothesis of no difference will be reported for each timepoint.

The number and proportion of subjects who achieve HbA1c reduction of $\geq 0.4\%$ will be summarized separately for Parts A and B by timepoint and treatment group. Reduction of $\geq 0.4\%$ is defined by the occurrence of a change from baseline which is less than -0.4% . A chi-square test will be conducted to compare the frequency observed in each of the two REMD-477 treatment groups versus the placebo group at each post-baseline timepoint.

